5.2.1. Study Procedures

5.2.1.1. Data Collection Study Equipment Set up

The following procedures will be performed for each study subject at study participation:

Assign an Apple Watch and the paired iPhone to each subject and document the Apple Watch and paired iPhone numbers and the version of Study App. The Watch configurations were selected at random from the total set of Watch configuration. The random assignment of watches to subjects is based on a pre-determined randomization schedule stratified by site, age group, and cohort.

1. Instruct the subject to choose his/her preferred wrist to wear the Apple Watch. The Apple Watch can be worn on whichever side the subject prefers unless there is a skin condition on one wrist as noted above in the exclusion criteria, in which case, the Apple Watch must be worn on the non-affected wrist. Record the chosen wrist. If the subject does not have a side preference or skin condition on one wrist, the device will be placed on the left wrist.
2. The subject will be asked to put the Apple Watch on his/her wrist (as indicated in 1). The Apple Watch should be fitted tightly enough that it does not move when the hand/wrist is shaken.
3. Check band tightness for a snug fit and adjust as needed.
4. Instruct the subject to read the provided instructions on how to Take an ECG. Instructions will come from the “How to Take an ECG” onboarding screen of the ECG app (DEN180044) on iPhone.
5. Ask the subject to take a practice ECG. After the first practice run, site study staff will guide subject to appropriate study posture and grip (if not achieved independently during the first test run).
6. Allow subject up to three additional practice runs if more practice runs are needed to ensure study posture and grip instruction understanding (fewer than 3 additional practice runs are acceptable if study posture and grip are correct and patient is comfortable with the positioning).

5.2.1.2. Data Collection – Rest ECG

1. Instruct subject to remain seated for a 5-minute resting period prior to collecting a 12-lead ECG and set the reference system to 40 Hz filter. Use standard placement of all 12-lead electrodes (with limb lead for Lead 1).
2. Collect a 12-lead ECG (review to ensure there is no artifact). The recording will be approximately 30 seconds in duration. Simultaneously, instruct the subject to record a separate complete single-lead ECG using the Apple Watch. Both data streams will be synced together by the Study Staff through a flash sync method.
 - a) Monitor the 12-lead ECG to ensure a good quality recording is obtained.
 - b) A total of three trials consisting of simultaneously recorded 12-lead ECG and single-lead ECG using the Apple Watch will be performed for each subject.
 - c) The first trial will be used for adjudication and analysis.
 - 
 - d) The baseline resting heart rate for exercise (5.2.1.3) will be determined from the 1st trial.

5.2.1.3. Exercise

For the exercise sessions, a target HR will be defined as 85% of predicted max HR (PMHR = 220 – age) which is not to exceed 150 bpm; thus the maximum target HR in any subject is 150 bpm. Subjects who have been cleared and deemed fit by the Investigator to exercise using the treadmill or stationary bike will complete training on how to use the exercise equipment and perform a practice session to determine adequate resistance for increasing the HR to > target HR. There will be up to 3 total exercise trials. Each trial consists of up to 5 minutes of exercise, depending on how long it takes for the target BPM of >target HR to be achieved, followed by an approximately 1 minute data capture session where the subject is stationary to complete a data capture session. Subject should be at target HR for at least 5 seconds prior to starting data collection. At the discretion of the investigator, blood pressure reading may be taken for safety purposes. During the exercise, the subject will be encouraged by the Study Staff to increase effort if the subject's initially chosen exercise intensity is too low to raise their HR by the requisite amount. For treadmill exercise, the subject is recommended to move off the treadmill and into a seated position, then supporting their arms and elbows on their lap while completing data collection with the Apple Watch. For stationary bikes, the subject can remain on the bike and place their hands on the bike handles in a still position for data collection with the Apple Watch.

The subject may rest in between each trial for approximately 3 minutes. The subject will be monitored throughout the session. The reference ECG will be continuously monitored during the exercise session by the Investigator and/or Study Staff.

The first trial will be used for adjudication and analysis. [REDACTED]

5.2.2. Apple Watch Data Processing

Apple Watches will be collected, data will be transferred from the Watches to the paired iPhones by CRO staff, and data will be transferred to study sponsor.

Procedures for ECG waveform generation and ECG app classification based on the collected Apple Watch sensor data are described in Section 9.1.

5.2.3. Adjudication of ECG Data

5.2.3.1. 12-lead ECG

Thirty second 12-lead ECGs will be reviewed by 2 independent US Board Certified Cardiologist adjudicators for heart rate and rhythm. In the event of discrepancy, ECGs will be reviewed by a third adjudicator. All adjudicators will be blinded to cohort, stage (resting or exercise) and ECG app classification. Adjudicators will be instructed to review ECGs independently and separately of each other and not to confer about diagnoses. The 12-lead ECGs generated from the first trial at rest and the first trial after exercise will be adjudicated for each subject.

For purposes of the primary endpoint analysis, the rhythm classification and the heart rate will be adjudicated separately. The final adjudicated rhythm classification result will be used if there is a rhythm classification discrepancy between the first two cardiologists.

5.2.3.1.1. Heart Rate

Heart rate will be calculated for each 12-lead ECG. Record the heart rate and select the heart rate diagnostic code that corresponds to the heart rate observed on the reference ECG. The final adjudicated heart rate result will be used if there is a heart rate discrepancy between the first two cardiologists.

5.2.3.1.2. Rhythm Diagnoses

The following rhythm diagnoses will be adjudicated to the 12-lead ECG data for each 12-lead ECG:

1. Sinus Rhythm (will include sinus bradycardia, normal sinus rhythm, and sinus tachycardia)
2. Atrial Fibrillation
3. Supraventricular tachycardia (SVT) with regular beat-to-beat intervals (e.g., AVNRT, AVRT, Atrial Tachycardia with HR over 100 beats per minute)
4. Other Abnormal Rhythm
 - a. Frequent Premature Atrial Contractions (>3 in 30 seconds)
 - b. Frequent Premature Ventricular Contractions (>3 in 30 seconds)
 - c. Atrial flutter
 - d. Ventricular tachycardia
 - e. Ventricular fibrillation
 - f. Second degree AV block, Type I
 - g. Second degree AV block, Type II
 - h. Third degree AV block
 - i. Other
5. Uninterpretable

5.2.3.1.3. Combining Heart Rate and Rhythm Diagnoses on 12-lead ECG

Table 5.1: Heart Rate and Rhythm Diagnoses on 12-Lead ECG

Heart Rate	Rhythm on 12-lead ECG				
	Sinus Rhythm	Atrial Fibrillation	SVT with regular intervals	Other	Uninterpretable
<50	HR<50	HR<50	N/A	HR<50	Uninterpretable
50-99	SR 50-99	AF 50-99	N/A	Other 50-99	Uninterpretable
100-150	SR 100-150	AF 100-150	SVT 100-150	Other 100-150	Uninterpretable
>150	HR>150	HR>150	HR>150	HR>150	Uninterpretable

5.2.3.2. ECG Strip Overlay

1. Strip preparation

- a. The Sponsor will prepare one paired set of at rest ECG strips from approximately 100 randomly selected subjects (50 AF; 50 SR) comprised of the Apple Watch ECG and lead 1 ECG from the 12-lead.

2. Cardiac Core Lab review:

- a. Three blinded, independent cardiac technicians will review each paired set of strips on 25mm/s, 10 mm/mV standard.
- b. One reviewer will identify the first six consecutive distinct readable PQRST complexes without artifact that match between the subject device strip and reference device strip for evaluation. For example, if the reference strip has an artifact in beats 2 and 5 but all other beats are good and the strip from the test device has artifact in beats 1 and 6 but all other beats are good, the six consecutive beats to be used will begin at beat 7 of both strips. The strips will be excluded if six consecutive beats cannot be found. The six PQRST complexes identified by the initial reviewer will be used by the 2 other reviewers.
- c. The strips will be rendered semi-transparent through the use of back lighting and overlaid to visually assess for morphological similarity.
- d. Each reviewer will assign a pass/fail to the strips by visually assessing all 6 PQRST complexes. A “pass” is given when the morphology of the PQRST complexes appears to overlay to the unaided eye.
- e. Measure R amplitude from the isoelectric baseline of the PR segment at the onset of the QRS complex to the highest vertical deflection of the R-wave. Measure to the nearest 0.5 millimeter for the first QRS complex of the six consecutive distinct readable PQRST complexes in both the reference strip and test device strip. The reviewers will be blinded to the identity of the reference strip and test device strip.

6. Study Endpoints

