**5.2.3.2. ECG Strip Overlay**

1. Strip preparation

- a. The Sponsor will prepare one paired set of rest ECG strips and one paired set of exercise ECG strips from 100 randomly selected subjects (50 AF; 50 SR). Each set of rest and exercise ECG strips will be comprised of the Apple Watch ECG and lead 1 ECG from the 12-lead.
2. Cardiac Core Lab review:
    - a. Three blinded, independent cardiac technicians or cardiologists will review each paired sets of strips on 25mm/s, 10 mm/mV standard.
    - b. One reviewer will identify the first six consecutive distinct readable PQRST complexes without artifact that match between the subject device strip and reference device strip for evaluation. For example, if the reference strip has an artifact in beats 2 and 5 but all other beats are good and the strip from the test device has artifact in beats 1 and 6 but all other beats are good, the six consecutive beats to be used will begin at beat 7 of both strips. The strips will be excluded if six consecutive beats cannot be found. The six PQRST complexes identified by the initial reviewer will be used by the 2 other reviewers.
    - c. The strips will be rendered semi-transparent through the use of back lighting and overlaid to visually assess for morphological similarity.
    - d. Each reviewer will assign a pass/fail to the strips by visually assessing all 6 PQRST complexes. A “pass” is given when the morphology of the PQRST complexes appears to overlay to the unaided eye.
    - e. Measure R amplitude from the isoelectric baseline of the PR segment at the onset of the QRS complex to the highest vertical deflection of the R-wave. Measure to the nearest 0.5 millimeter for the first QRS complex of the six consecutive distinct readable PQRST complexes in both the reference strip and test device strip. The reviewers will be blinded to the identity of the reference strip and test device strip.

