Because data will be collected from the same subjects at rest and after exercise, a bootstrap approach will be implemented to obtain two-sided 95% confidence intervals for the percent correct associated with each of the four secondary endpoint hypotheses to account for potential within-subject correlation. Subjects with at least one adjudicated result of SR (HR 50-99) [hypothesis 2a], AF (HR 50-99) [hypothesis 2b], SR (HR 100-150) [hypothesis 2c], AF (HR 100-150) [hypothesis 2d] and with a classifiable algorithm result will be selected at random with replacement and the 2.5th and 97.5th percentiles of the distribution of bootstrap estimates will represent the two-sided 95% confidence bounds. If the lower confidence bound of the percent correct equals or exceeds the pre-established performance goal associated with the associated secondary endpoint hypotheses, the null hypotheses will be rejected in favor of the alternative hypotheses.

Additional secondary endpoint analyses will be performed similarly by including the HR < 50, HR > 150, and Inconclusive algorithm results in the computations of percent correct.

Two hypotheses associated with secondary objective to demonstrate that the ECG app produces a waveform that provides clinically equivalent information to Lead 1 of the 12-Lead ECG will be tested.

The first hypothesis is aimed at demonstrating that the proportion of subjects with a morphology pass rating based on the visual assessment of 6 consecutive readable PQRST complexes is at least [REDACTED]. The majority result from the pass/fail readings of the 3 independent, certified cardiac technicians will be used for analysis. The hypothesis for this objective is stated as follows:

[REDACTED]  
[REDACTED]

The second hypothesis will be based on the results of the quantitative analysis of the R-wave amplitudes as measured by each of 3 independent, certified cardiac technicians on the paired ECG app and Lead 1 from the 12-Lead ECG reference strips. The majority result from the three

technicians (i.e., if at least two technicians measured the difference in amplitudes between the SUT and reference strips to be  $\leq 2$  mm then the paired strips for a given subject were deemed  $\leq 2$  mm) was used for [REDACTED]

For each subject, the QRS complex from the 12-lead ECG with the largest R amplitude (out of the two QRS complexes with R-wave amplitude measurements) will be used for purposes of determining the majority result.

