Data from the first trial run of the randomly selected subjects while the subject is at rest and after exercise will be used to test the two waveform assessment hypotheses using a bootstrap sampling approach. If the 2.5th percentile of the bootstrap distribution for the Morphology Pass Rating Proportion [REDACTED] the null hypothesis  $H_{0\_2e}$  will be rejected. [REDACTED] to the evaluation of the R-Wave Amplitude Agreement Proportion.

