Because data will be collected from the same subjects at rest and after exercise, a bootstrap approach will be implemented to obtain two-sided 95% confidence intervals for the percent correct associated with each of the four secondary endpoint hypotheses to account for potential within-subject correlation. Subjects with at least one adjudicated result of SR (HR 50-99) [hypothesis 2a], AF (HR 50-99) [hypothesis 2b], SR (HR 100-150) [hypothesis 2c], AF (HR 100-150) [hypothesis 2d] and with a classifiable algorithm result will be selected at random with replacement and the 2.5th and 97.5th percentiles of the distribution of bootstrap estimates will represent the two-sided 95% confidence bounds. If the lower confidence bound of the percent correct equals or exceeds the pre-established performance goal associated with the associated secondary endpoint hypotheses, the null hypotheses will be rejected in favor of the alternative hypotheses.

Additional secondary endpoint analyses will be performed similarly by including the HR<50, HR>150, and Inconclusive algorithm results in the computations of percent correct.

Two hypotheses associated with secondary objective to demonstrate that the ECG app produces a waveform that provides clinically equivalent information to Lead 1 of the 12-Lead ECG will be tested.

[REDACTED]

The majority result from the pass/fail readings of the 3 independent, certified cardiac technicians will be used for analysis. The hypothesis for this objective is stated as follows:

[REDACTED]

[REDACTED]

The second hypothesis will be based on the results of the quantitative analysis of the R-wave amplitudes as measured by each of 3 independent, certified cardiac technicians on the paired ECG app and Lead 1 from the 12-Lead ECG reference strips. The majority result

from the three technicians (i.e., if at least two technicians measured the difference in amplitudes between the ECG app and reference strips to be ≤ 2 mm then the paired strips for a given subject were deemed ≤ 2 mm) was used [REDACTED]

[REDACTED]

[REDACTED]

[REDACTED]

For each subject, the QRS complex from the 12-lead ECG with the largest R amplitude (out of the two QRS complexes with R-wave amplitude measurements) will be used for purposes of determining the majority result.

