Due to the multiple observations per subject while at rest and during exercise, a bootstrap approach will be used to construct two-sided 95% confidence intervals for the Morphology Pass Rating Proportion and the R-Wave Amplitude Agreement Proportion. If the lower 2.5th percentile of the bootstrap distribution for the Morphology Pass Rating Proportion [REDACTED], the null hypothesis $H_{0,2e}$ will be rejected. [REDACTED] to the evaluation of the R-Wave Amplitude Agreement Proportion.

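### SAP 5.2.3.2 prepares at-rest strip pairs only, against the protocol and SAP 9.7; followed literally, waveform endpoints 2e and 2f would have no post-exercise data

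*SAP*

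**What the plan says.** **Preparing the strips.** SAP 5.2.3.2, strip preparation, reads: "The Sponsor will prepare one paired set of at rest ECG strips from approximately 100 randomly selected subjects (50 AF; 50 SR"). No exercise set is mentioned. The same step in Protocol 5.2.3.2 calls for "one paired set of rest ECG strips and one paired set of exercise ECG strips from 100 randomly selected subjects".

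**Analysing the strips.** Protocol 6.2.2 says that first-trial data "while the subject is at rest and after exercise will be used to test the two waveform assessment hypotheses". SAP 9.7 gives this reason for its method: "Due to the multiple observations per subject while at rest and during exercise, a bootstrap approach will be used". For R-wave amplitude, SAP 9.7 takes for each subject the 12-lead complex "with the largest R amplitude (out of the two QRS complexes with R-wave amplitude measurements").

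**Measuring the strips.** Step e of the core-lab review in SAP 5.2.3.2 reads: "Measure to the nearest 0.5 millimeter for the first QRS complex of the six consecutive distinct readable PQRST complexes". It applies to the reference strip and to the test strip, so each strip yields one measured complex.

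**Related text.** SAP 7.2 blinds the technicians to stage. SAP 11 declares that enrolment stopped early, that race categories were collapsed, and that the scheme for selecting waveform subjects was revised. It otherwise says that analyses go ahead as planned.

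**The concern.** The strip-preparation sentence is the SAP's only instruction on which tracings go to the core lab, and it names one stage. The analysis section of the same document assumes two. The SAP reports the March 2020 enrolment stop, so it is later than the December 2019 protocol. Its overlay section also differs from the protocol in other small ways: the subject count is approximate, and the readers are technicians only. A reader therefore cannot tell whether rest-only is a slip or a decision.

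Two tested secondary endpoints are at stake. Protocol 6.3 and SAP 7.1 give the purpose of the waveform sample as checking equivalence over varied heart rates and rhythms. Exercise is the stage designed to produce the higher rates. Without it, endpoints 2e and 2f say nothing about tracings taken after exertion, and they estimate a different quantity from the one the protocol tests.

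**Working it through.** **1. The plan's own figure.** The sample of about 100 subjects cannot be derived, because the goals and expected proportions for 2e and 2f are redacted. It is not disputed here. Applied to planned enrolment, the SAP intervals give 400/6 + 168/5 = 66.7 + 33.6 = 100.3 subjects, and the protocol intervals give 400/6 + 168/3 = 66.7 + 56 = 122.7. SAP 11 says its interval was reset for the smaller number actually enrolled, which is not given. These figures therefore only confirm the order of size.

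**2. The passages side by side.**

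| Place | Stages |
|---|---|
| Protocol 5.2.3.2, preparation | rest and exercise |
| Protocol 6.2.2, analysis | rest and exercise |
| SAP 5.2.3.2, preparation | rest only |
| SAP 9.7, analysis | rest and exercise |
| SAP 7.2, blinding to stage | both, by implication |
| SAP 11, declared changes | which subjects are selected; nothing on stage |

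The conflicting sentences are legible, so redaction does not explain the difference.

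**3. Strip pairs.** Protocol: 100 × 2 = 200 pairs, 100 of them post-exercise. SAP sentence taken literally: 100 × 1 = 100 pairs, 0 of them post-exercise.

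**4. The R-wave rule.** There is one measured complex per strip and one 12-lead strip per stage. Two stages give 2 reference complexes per subject; rest only gives 1. A rule that takes the larger of two then has nothing to choose between. With one pair per subject, the reason SAP 9.7 gives for the bootstrap also disappears.

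**5. Heart rates that exercise is meant to supply.** SAP 5.2.1.3 says "a target HR will be defined as 85% of predicted max HR", with predicted maximum 220 − age and a cap of 150 bpm. Target = min(150, 0.85 × (220 − age)):

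- age 43: 0.85 × 177 = 150.4, capped at 150
- age 55: 0.85 × 165 = 140.2
- age 65: 0.85 × 155 = 131.8
- age 80: 0.85 × 140 = 119.0

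The target exceeds 100 bpm up to age 220 − 100/0.85 = 102.4. These are targets, not achieved rates.

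**6. Shift in 2e (illustration).** Assume analysis by strip pair and equal numbers of readable pairs per stage. Then rest-only minus pooled = p_rest − (p_rest + p_ex)/2 = (p_rest − p_ex)/2. For assumed gaps of 0, 2, 5 and 10 points, the shift is 0, 1, 2.5 and 5 points. The documents give no gap. No figure is offered for 2f, because the shift depends on how often the larger R wave occurs after exercise, which is not stated.

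**7. Precision (illustration).** Half-width = 1.96 × √(p(1 − p)/n_eff), with n_eff = 100 for rest only and 200/(1 + ρ) for two pairs per subject, where ρ is the within-subject correlation. At an assumed p of 0.95, rest only gives 4.3 points. Both stages give 3.0 at ρ = 0, 3.7 at ρ = 0.5 and 4.3 at ρ = 1. The certain loss is post-exercise coverage; the loss of precision depends on ρ.

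**The case against.** The strongest reply is that this is a slip in a section that restates protocol procedures. The protocol's preparation step, the protocol's analysis and the SAP's analysis all use both stages, and SAP 11 says analyses proceed as planned. Nothing shows that the core lab works from the SAP. Only two secondary endpoints are touched. The stage-blinding text matches the protocol's and may simply have been carried over. Resting AF strips can include rates of 100–150 bpm, so not all high-rate coverage would be lost. The R-wave argument rests on reading the two complexes as rest and exercise, and redacted text stands just before that rule.

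Much of this stands. The harm is conditional, the blinding text is weak evidence, and some high rates may occur at rest. The reading of the R-wave rule is the natural one given one complex per strip, but it is not confirmed. It also brings a tension of its own: one 2f result per subject does not fit a bootstrap justified by multiple observations.

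None of this removes the conflict. The two analysis sections and the protocol's preparation step cannot be met from the strips the SAP tells the sponsor to prepare. High rates in some resting AF strips do not replace post-exercise tracings. Calling it a slip is a guess about intent in a later document whose overlay section was changed elsewhere too.

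**Conclusion.** The concern holds. As written, the SAP's preparation step contradicts its own analysis section and the protocol, and the difference is not declared. Taken literally, it gives 0 exercise pairs instead of up to about 100, and one reference complex per subject where the R-wave rule chooses between two. Endpoints 2e and 2f would then be rest-only estimates.

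This assumes that the core lab follows the SAP sentence. The figure of about 100 is the stated target; the number actually selected after enrolment stopped is not given. The size of any shift in 2e rests on an assumed difference between stages. Whether it would change the endpoint decision cannot be shown. The co-primary endpoints and 2a–2d are unaffected. It should be corrected before strips are read, but it does not threaten the study's main conclusions.

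**What to change.** Before any strips are read, change the preparation sentence in SAP 5.2.3.2 so that the sponsor prepares a rest pair and an exercise pair for each of about 100 selected subjects, each pair made up of the watch tracing and lead I. Keep the count approximate, since enrolment ended early. If rest-only was intended, declare and justify it in SAP 11 and align SAP 7.2 and 9.7.

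In the same edit, unless redacted text already does so:

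- Say which two complexes the R-wave rule chooses between. If they are rest and exercise, state that 2f then uses one stage per subject.
- Reconcile the unit of analysis. Protocol 6.2.2 words 2e as "the proportion of subjects with a morphology pass rating", and the R-wave rule gives one result per subject, while SAP 9.7 bootstraps both endpoints for multiple observations per subject.

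The cost is one SAP sentence and a short clarification in SAP 9.7. Restoring both stages needs no protocol amendment and no new recordings: Protocol 5.2.3.2 already plans the exercise strip sets, and the exercise tracings are part of the planned data collection.

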6.2. Secondary Endpoints

2a. Correct classification of subjects with normal sinus rhythm (HR 50-99, sinus rhythm (SR) on simultaneous 12-lead ECG) as “Sinus Rhythm” on a readable and classifiable ECG app strip

2b. Correct classification of subjects with AF (HR 50-99, AF on simultaneous 12-lead ECG) as “AF” on a readable and classifiable ECG app strip

[figure not shown]
2c. Correct classification of subjects with sinus tachycardia (HR 100-150, SR on simultaneous 12-lead ECG) as “High Heart Rate” on a readable and classifiable ECG app strip

[figure not shown]
2d. Correct classification of subjects with AF with high heart rate (HR 100-150, AF on simultaneous 12-lead ECG) as “AF (high heart rate)” on a readable and classifiable ECG app strip

2e. Equivalence of the ECG app waveform to Lead I from a 12-lead ECG as measured by acceptable morphology of PQRST complexes

2f. Equivalence of the ECG app waveform to Lead I from a 12-lead ECG as measured by R-Wave amplitude agreement

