7.6. Interim Analyses

There are no interim analyses planned in this study.

8. Analysis Sets

The following analysis sets are defined for this study.

Full Analysis Set (FAS): All subjects who sign informed consent and are enrolled into the study. This analysis set will be used to summarize subject 12-Lead, and ECG app device accountability in addition to demographic and baseline characteristics and safety data. The data for this analysis set will be presented overall and separately for the enrollment cohorts.

Classifiable Analysis Set (CAS): All subjects who have readable paired ECG app and 12-Lead ECG adjudicated results. This analysis set will be used for analyzing the co-primary endpoints (1a, 1b), the four secondary endpoints (2a, 2b, 2c, and 2d) and the additional analyses.

Waveform Assessment Analysis Set (WAAS): Randomly selected subjects with readable paired strips from the ECG app and Lead 1 of the 12-Lead ECG. If 6 consecutive beats for analysis cannot be found in these strips, they will be excluded from further analysis. This analysis set will be used for assessing the clinical waveform accuracy associated with secondary endpoints 2e and 2f.

9. Analysis Approach

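### Endpoints 2e and 2f drop pairs whose watch strip alone lacks six clean beats, and no planned analysis or table shows how much this raises the waveform proportions

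*SAP*

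**What the plan says.** Protocol 5.2.3.2 and SAP 5.2.3.2 describe the same core-lab steps. One reviewer, looking at both strips, finds the "first six consecutive distinct readable PQRST complexes without artifact that match between the subject device strip and reference device strip". In the worked example the reference has artifact in beats 2 and 5 and the test strip in beats 1 and 6, so "the six consecutive beats to be used will begin at beat 7 of both strips".

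That selection then binds everyone: "The six PQRST complexes identified by the initial reviewer will be used by the 2 other reviewers". The selector also grades: "Each reviewer will assign a pass/fail to the strips by visually assessing all 6 PQRST complexes". The result for 2e is the majority of three readings. The amplitude for 2f is measured on the first of the same six beats, so one selection step feeds both endpoints.

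The Protocol item ends: "The strips will be excluded if six consecutive beats cannot be found". The Waveform Assessment Analysis Set (WAAS; Protocol 6.8, SAP 8 Analysis Sets) consists of "Randomly selected subjects with readable paired strips from the ECG app and Lead 1 of the 12-Lead ECG", and the SAP adds: "If 6 consecutive beats for analysis cannot be found in these strips, they will be excluded from further analysis". The missing-data sections (Protocol 6.5, SAP 7.4) keep to analyzable data. No rule treats an excluded pair as a failure.

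The rhythm endpoints are handled differently. Protocol 6.2.1 and 6.2.2 and SAP 9.6 and 9.7 give endpoints 1a to 2d additional analyses that put Inconclusive results back into the denominator.

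**The concern.** Endpoint 2e is worded as "Equivalence of the ECG app waveform to Lead I from a 12-lead ECG as measured by acceptable morphology of PQRST complexes", and Protocol 6.2.2 and SAP 9.7 link 2e and 2f to the aim of showing that the app's waveform is clinically equivalent to Lead I. When the reference strip has six clean beats and the simultaneous watch strip does not, that recording bears on the claim, and it bears against the watch. Under the plan it disappears from both numerator and denominator.

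The loss probably works in one direction. A watch strip too noisy to yield six clean beats is unlikely to be one that would have overlaid well. If so, the reported proportions describe retained pairs and overstate agreement across all selected pairs. The documents show no way to judge the extent, because no table separates waveform exclusions by the strip at fault.

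**Working it through.** **1. Does the rule do what it appears to do?** In the worked example, the beats with artifact on either strip are 1, 2, 5 and 6. The first run of six consecutive beats avoiding all four is 7 to 12, which agrees with the documents. The filter uses artifact on either strip, so watch-side artifact alone can move the window or remove the pair.

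**2. Where do removed pairs go?**

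| Endpoint | Results left out of the main analysis | Analysis that restores any of them |
|---|---|---|
| 1a, 1b | Inconclusive, Poor Recording | Inconclusive restored (Protocol 6.2.1, SAP 9.6) |
| 2a to 2d | HR<50, HR>150, Inconclusive, Poor Recording | First three restored (Protocol 6.2.2, SAP 9.7) |
| 2e, 2f | Pairs without six common clean beats | None |

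Inconclusive and Poor Recording counts are tabulated (Protocol 6.2.4, SAP 9.8), but these are algorithm outputs and not WAAS exclusions.

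**3. Upper limit on the bias.** Let N be the pairs selected, d the fraction dropped and x the passes among those kept. The reported proportion is x/[N(1-d)]. If every dropped pair would have failed, the all-pairs proportion is x/N. The ratio is 1/(1-d), and it is smaller if some dropped pairs would have passed.

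**4. Illustration.** The plan gives about 100 subjects (50 SR, 50 AF) and a one-sided level of 0.025. The sample size cannot be reproduced, because its goal, expected rate and required number are redacted. Assumptions: 100 pairs, one per subject; about 98% of kept pairs pass; every drop is due to the watch strip alone and counted as a failure. In brackets is the exact binomial one-sided 97.5% lower bound, standing in for the planned bootstrap percentile.

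| Dropped | Kept pairs only | Drops counted as failures |
|---|---|---|
| 0 | 98/100 = 98.0% (93.0%) | 98/100 = 98.0% (93.0%) |
| 5 | 93/95 = 97.9% (92.6%) | 93/100 = 93.0% (86.1%) |
| 10 | 88/90 = 97.8% (92.2%) | 88/100 = 88.0% (80.0%) |

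Check for five dropped: 1/(1 - 0.05) = 1.053, and 97.9%/1.053 = 93.0%.

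**5. Could it change a conclusion?** For assumed goals of 80%, 85% and 90%, the two columns first disagree at 10, 6 and 3 dropped pairs. Using the 2.5th percentile of a simple bootstrap (the 2.5% binomial quantile divided by n, with the goal to be strictly exceeded), they first disagree at 11, 7 and 3. Both sets depend on assumed goals and on the worst case for dropped pairs.

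**The case against.** There is a good case for the plan. The window must be the first that qualifies, the artifact rule treats the two strips alike, readers are blinded to strip origin, and the selector has one vote of three. Conditioning on readable beats is openly pre-specified. Whether interpretable beats look alike and how often a recording is uninterpretable are different questions. Even the additional analyses for 1a and 1b leave Poor Recording out. A 30-second strip at 50 to 150 bpm holds 25 to 75 beats, of which only six clean consecutive ones are needed, so losses may be few.

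These points limit the reviewer's discretion and support keeping the current rule for the main analysis. They do not answer the denominator question, because an excluded pair never reaches a vote.

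Four stronger readings are tempting, and the documents do not support them.

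- A reader might infer that the matching condition selects beats for similar shape, so that the outcome is built into the selection. The word is undefined, but the only example selects on artifact and beat number, and the recordings are simultaneous and synchronised (Protocol and SAP 5.2.1.2). The same beats in time is the natural meaning.
- A reader might infer from the endpoint wording that 2e has no readability condition. Protocol 6.2.2 bases its hypothesis on six consecutive readable complexes; the parallel SAP text is redacted.
- A reader might infer that noisy post-exercise strips are the ones being lost. SAP 5.2.3.2 prepares rest strips only, while Protocol 5.2.3.2 and 6.2.2 and SAP 9.7 use rest and exercise. Coverage must be settled first.
- A reader might infer that every exclusion is a watch failure. Reference artifact also removes pairs.

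**Conclusion.** The point holds in a limited form. Pairs lost to the watch strip alone are dropped from 2e and 2f, no analysis counts them, and no visible table would reveal how many there were. Upward bias relative to all selected pairs follows if dropped pairs would pass less often than kept ones. That is plausible but cannot be verified from the documents. The bias is at most a factor of 1/(1-d). In the illustration it is 4.9 percentage points (97.9% against 93.0%) at five watch-only losses in 100, and that is a worst case on assumed figures.

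The actual size is unknown, and the documents do not show that the exclusions would decide either test. These are secondary endpoints. The gap justifies a cheap pre-specified check, not a new selection rule.

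**What to change.** 1. Keep the current rule for the main analysis. In item 2b of both documents, state that matching beats are the same time-aligned beats on the two strips, not beats of similar shape.
2. For each excluded pair, have the blinded selecting reviewer record which masked strip (A, B or both) lacked six clean beats. Unmask this only at analysis.
3. Add to SAP 9.7 a sensitivity analysis that counts pairs lost to the watch strip alone as fail for 2e and not in agreement for 2f. With k pairs kept, w lost to the watch alone and x passing, report x/(k + w) with the same bootstrap interval. Pairs lost to the reference or to both strips stay excluded.
4. Tabulate WAAS exclusions by strip at fault, cohort and stage.
5. Reconcile the rest-only preparation in SAP 5.2.3.2 with the rest-plus-exercise text in Protocol 5.2.3.2 and 6.2.2 and SAP 9.7. This settles whether there are about 100 or about 200 pairs and so defines the denominator.

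Do not have a grading reviewer choose beats from the reference strip alone. That reveals which strip is the reference and breaks the blinding to origin in Protocol 3.4, SAP 7.2 and item 2e of 5.2.3.2.

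The cost is one extra core-lab field, one table and one analysis, with the same readers and strips. The sensitivity proportion may be less favourable than the main one.
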